6.4.2 Treatment Administered

Eligible patients will be randomly assigned to one of the two following treatment groups:

Treatment period

- Group !
 - Gerdoff®: CS, HA and aluminium hydroxide chewable tablets.

Route of administration: oral

Dosage regimen: one tablet three times daily: 1 tablet after breakfast, 1 tablet after lunch and 1 tablet in the evening before retiring to bed.

Treatment duration: 6 weeks \pm 2 days.

- Omeprazole (proton pump inhibitor, PPI)

Route of administration: oral.

Dosage: two 20 mg capsules once daily in the morning before breakfast.

• Group 2

- Omeprazole (proton pump inhibitor, PPI)

Route of administration: oral.

Dosage: two 20 mg capsules once daily in the morning before breakfast.

Treatment duration: 6 weeks \pm 2 days.

Follow-up period

During the 12-week follow-up period, which started from the end of study visit V4, responder patients of Group 1 will be randomly assigned to receive treatment with Gerdoff®, according to the above reported dosage, or will be assigned to the control group and will be therefore not treated. All patients received a packaging of omeprazole, to be taken only if necessary, at constant dose and according to the indications of the Investigator.

The scheduled duration of the follow-up period will be 12 weeks \pm 3 days for both treatment groups.

Administration of investigational products

• Study period

Patients will be instructed to take, starting from the morning of the day following Visit V1, the investigational products every day for the next 6 weeks.

• Follow-up period

Patients will be instructed to take, starting from the morning of the day following Visit V4, the investigational products every day for the next 12 weeks.

6.4.3 Selection of Doses of the Investigational Device

The dose regimen of Gerdoff[®] used in the present study (i.e. one tablet three times daily: 1 tablet after breakfast, 1 tablet after lunch and 1 tablet in the evening before retiring to bed) is that scheduled in the marketed package insert of the product for adults and children over 12 years.

6.4.4 Selection of Timing and Dose for Each Patient

Refer to Section 6.4.3

6.4.5 Compliance and Device Accountability

Patients will be instructed to record in the daily diary the amount of investigational products taken during the entire study period, highlighting that the administered quantity will be not to be lower than that scheduled for the study to not invalidate the efficacy of treatment.

At the end of the study, the Investigator counted the amount of tablets and of capsules returned by the patient and compared this amount with the quantities reported in the patient daily diary. In case of discrepancies, clarifications will be asked to the patient and will be reported in the clinical records/worksheet and in the eCRF.

The study monitor counted the returned investigational products and compared the returned quantity with the use reported in the patient diary to assess the patient's adherence to the scheduled dosage.

Patients with values of compliance $\geq 95\%$ of the overall dosage scheduled in the 6-week treatment period, evaluated on the basis of minimal taken daily dose, will be considered as adherent to treatment

6.4.6 Prior and Concomitant Medications

At the baseline visit, the Investigator instructed the patients on the use of rescue medication, and on the list of permitted and non-permitted concomitant medications.

Permitted concomitant medications

With the exception of those drugs listed among non-permitted medications, participants will be allowed to use any concomitant medication necessary for the treatment of pre-existing concomitant pathologies or for intercurrent diseases, provided that they will not interfere with study evaluation parameters and that it will be not taken for the treatment of GERD.

Rescue medication

During the first 6 weeks of treatment, the use of any type of rescue medication, i.e. the intake of any other therapy for GERD irrespective from the dose and frequency of administration, will be to be considered as a protocol violation. In the event of intake of non-permitted medications, the Investigator had to decide whether it will be the case for maintaining the patient into the study, even if it will be considered as a protocol violator. The administered treatment will be to be recorded in the source documentation and in the eCRF.

During the follow-up period, (V4-V6), in case of worsening of symptoms, the use of omeprazole (PPI) will be permitted as rescue medication at constant dose, both in patients included in the control group and in those included in the Gerdoff® group. The administration of omeprazole will be to be recorded in the source documentation and in the eCRF.

In the case of use of any other product taken as rescue medication for the control of GERD, patients will be to be considered as protocol violators and will be to be discontinued from the study. The possible intake of any other PPI different from omeprazole, the change in dosage or the intake of other rescue medications will be to be recorded in the source documentation and in the eCRF.

Non-permitted concomitant medications

The following medications will be not permitted during the whole study period:

- Chronic use of drugs that interfere with the salivary secretion (e.g. anti-histamines of inhaled steroids) and previous use of PPIs and/or medical devices and/or similar products (e.g. alginates, antacids etc..) in the 4 weeks preceding the inclusion in the study;
- During the first 6-week treatment period, the use of any type of rescue medication will be not permitted, as well as the use of any other therapy for GERD, irrespective of dosage and frequency of administration. In case of intake of any type of rescue medication, patients will be to be considered as protocol violators;
- During the follow-up period only the use of omeprazole will be permitted as rescue medication at constant dose, to be taken only if necessary and according to the indications of the Investigator. The administration of any other therapy for GERD will be not permitted.

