2.2 Secondary Objectives

The secondary objectives of the study will be to assess:

- The number and percentage of responders/non-responders at visit V4, after 6 weeks of treatment with Gerdoff®-PPI/PPI;
- The number and percentage of patients that maintained the effect of treatment at the follow-up visit V6, compared to the end of study visit V4, after 12 weeks of treatment with Gerdoff® or no treatment (control group);
- The percentage of reduction of symptoms' frequency in the two treatment groups, by means of a Likert questionnaire, at visit V4 after 6 weeks of treatment compared to baseline, and at visit V6 after 18 weeks of treatment compared to Visit V4;
- The overall patient's satisfaction of treatment, by means of a semiquantitative scale;
- The concomitant use of permitted and non-permitted rescue medications, during the first 6 weeks of treatment and the follow-up period;
- The safety of investigational products, evaluated by means of recording of changes in safety haematology and blood chemistry parameters and by collecting possible incidents/adverse events occurred during:
 - The first 6 weeks of treatment, for patients included in Group 2, PPI only, and for non-responder patients included in Group 1 (Gerdoff®-PPI);
 - During the overall 18-week study period for patients that continued with the follow-up period.

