6.3.3 Removal of Patients from Therapy or Assessment

Patient withdrawal

Patients had the right to withdraw from the study at any time for any reason including personal reasons (consent withdrawal). The Investigator also had the right to withdraw any patient from the study if he/she deemed this appropriate and in the best interest of the patients.

The following necessitated the discontinuation of a patient from the study:

- Voluntary subject withdrawal for any reason, even if not motivated;
- Appearance of an adverse event that could put at risk the patient's health;
- Sponsor's decision (to be justified);
- Investigator's decision (to be justified), in the patient's best interest;
- Poor patient's compliance to scheduled study visits and/or study procedures,
- Worsening of clinical general conditions requiring the discontinuation of the study;

- Major protocol violations (e.g. intake of any other therapy for GERD, irrespective of dose and frequency of administration);
- Poor adherence to inclusion/exclusion criteria that emerged after the inclusion of a patient and that will not guarantee the patient's safety.

The reasons for the interruption or the exclusion of a patient from the study had to be reported in the eCRF section 'End of study form' or 'End of follow-up period form' and will be to be communicated to the study sponsor.

In the case of early study discontinuation, the patient will be to be considered as a treatment failure. However, the investigator had to make any effort to perform the end of study assessments, scheduled at visit V4, in case a patient interrupted the study during the 6-week treatment period, or scheduled at visit V6, in case a patient interrupted the study during the 12-week follow-up period.

In the discontinuation visit, the patient had to return the investigational product and the daily diary completed up to the time of discontinuation.

The investigator had to record the reasons for the patient's treatment discontinuation and the early study conclusion in the clinical record/worksheet and in the eCRF. The sponsor had to be timely informed.

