- Ouring the first 6 weeks of treatment the use of any type of rescue medication will be not permitted in both treatment groups. The possible intake of rescue medication during the first 6 weeks of the study will be to be considered as a protocol violation. During the follow-up phase only the use of omeprazole as rescue will be permitted as rescue medication, at constant dose and only if necessary, in both the group of untreated patients (control group) and the group of treated patients, whereas the use of other products for the treatment of GERD will be not permitted. In case of intake patients will be to be considered as protocol violators and will be to be discontinued from the study. The possible rescue medications used during the overall study period will be to be recorded in the source documentation and in the eCRF.
- (c) In case of early study discontinuation the patient will be to be considered as a treatment failure and the investigator had to do all the possible to perform:
 - End of study assessments, scheduled at visit V4, in case the patient interrupted the study during the 6-week treatment period;
 - End of follow-up period assessments, scheduled at visit V6, in case the patient interrupted the study during the 12-week follow-up period.
- (d) Visit V5 could be also performed as phone visit, only if agreed with the patient at Visit V4, during which the Likert scale and the RSI questionnaire for the visit V5 and the daily diaries for the visits V5 and V6 will be to be handed to the patient. At visit V6, the patient had to return them to the Investigator.

Study periods

The study plan included two consecutive study periods:

Treatment period

From Visit V1 to Visit V4, in which randomised patients took Gerdoff® + PPI (omeprazole) or PPI (omeprazole) for a period of 6 weeks. During the treatment period patients attended 4 scheduled visits: Visit V1 will be the baseline visit for patients' inclusion in the study, Visits V2 and V3 will be intermediate visits for the evaluation of the effects of treatment, and Visit V4 will be the end of study visit in which patients will be classified as responders or non-responders.

• Follow-up period

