6.5.3 Study Endpoints

Primary performance variable

The primary performance variable of the study will be the change from baseline to visit V4 of the total score of RSI questionnaire, used to assess the effect of treatment on upper symptoms. The RSI questionnaire examines 9 items, to be scored from 0 to 5, with a higher score indication a higher severity of the symptom (range of total score: 0-45).

Secondary performance variables

The secondary performance variables of the study will be:

- Change of the total score of RSI questionnaire from baseline to the other time points;
- Change of the score of single items of the RSI questionnaire from baseline at any time point;
- Number and percentage of responder/non-responder patients at end of treatment (visit V4);
- Change from baseline to end of treatment (visit V4) and end of follow-up (visit V6) of upper symptoms, assessed using the Likert scale. The Likert scale scored symptoms from 0 to 4, with a higher score indication a higher frequency of the symptom;
- Presence of upper symptoms at baseline, end of treatment (visit V4) and end of follow-up (visit V6), assessed using the RSI questionnaire and the Likert scale:
- Use of rescue medication during the follow-up period: administered therapy, frequency of administration, timing of administration and administered dose;
- Patient's opinion of satisfaction with treatment, requested at intermediate Visits V2 and V3, and at the end of treatment visit V4, by means of a semiquantitative ordinal scale, where: 0 = low, 1 = discrete, 2 = good, 3 = excellent.

Safety variables

The safety variables of the study will be:

- Frequency of adverse events and incidents occurring at any time, during the study;
- Changes from baseline of haematology and blood chemistry parameters;
- Changes from baseline of vital signs (weight, BMI, blood pressure, heart rate and respiratory rate).

Incidents and adverse events

Incidents

According to MEDDEV 2.12.1, Rev. 8, a medical device incident is defined as 'any malfunction or deterioration in the characteristics and/or clinical performance of a device, as well as any inadequacy in the labelling or the instructions for use, which, directly or indirectly, might lead to or might have

led to the death of a patient, or a user or of other persons or to a serious deterioration in their state of health'.

A medical device incident that required reporting included:

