8.2 Populations for Analysis

All efficacy and safety analyses will be conducted on the Intent-to-Treat population (ITT), defined as all randomized patients in the first period of study (first 6 weeks) who took at least one study treatment dose.

In addition to the primary analysis carried out on the ITT population, some secondary sensitivity analyses will be carried-out in accordance with the criteria mentioned above. The sensitivity analyses will be implemented according to the following criteria:

- Considering that a minimum intake of study treatment will be required for the assessment of the efficacy of therapy on the primary objective, it will be considered that evaluable patients on the primary end-point had taken at least 95% of the total dosage in the 6-week treatment period, as foreseen in the study protocol. Patients who will not reach this target will be excluded from the primary analysis, but entered in the sensitivity analysis to confirm the efficacy of treatment with Gerdoff® in the improvement of the high symptoms.
- Patients who took not allowed rescue medication will be excluded from the sensitivity analysis on the primary end-point.
- Patients who took drugs that interfere with salivary secretion remained included in the sensitivity
 analyses by derogation from the study protocol, since during the data review meeting the
 clinicians considered as not significant the interference of these drugs on the response of the
 primary variable.
- Patients who had a worsening of the upper symptoms and required an additional therapy or a modification of the dosage of omeprazole taken compared to the protocol during the 6-week

treatment period, according to the Investigator's opinion, will be considered major violators but remained in the study until visit V4 and entered into the ITT efficacy analysis. Such patients will be considered as non-responders in the analysis of the follow-up phase.

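### In follow-up, taking any GERD product other than omeprazole ends data collection, so later rescue use and on-schedule week-18 scores are lost for the patients who do so

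*Combined protocol and SAP*

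**What the plan says.** **The removal rule.** For V4 to V6, section 6.4.6 permits omeprazole as rescue in both arms. For any other product taken as rescue it says "for the control of GERD, patients will be to be considered as protocol violators and will be to be discontinued from the study". The rescue note to the flow-chart in section 6.5.1 repeats this: "In case of intake patients will be to be considered as protocol violators and will be to be discontinued from the study".

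**The threshold.** Section 6.3.3 lists, among the events that require discontinuation, "Major protocol violations (e.g. intake of any other therapy for GERD, irrespective of dose and frequency of administration". One intake is therefore enough.

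**What happens to data.** At the discontinuation visit "the patient had to return the investigational product and the daily diary completed up to the time of discontinuation" (section 6.3.3). The investigator must try to obtain the assessments "scheduled at visit V6, in case a patient interrupted the study during the 12-week follow-up period". The patient counts as a treatment failure. Section 6.4.7 bars re-entry, and no later contact is described.

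**What the plan wants to measure.** Section 2.2 lists as an objective "The concomitant use of permitted and non-permitted rescue medications, during the first 6 weeks of treatment and the follow-up period". Section 6.5.3 lists as an endpoint "Use of rescue medication during the follow-up period: administered therapy, frequency of administration, timing of administration and administered dose". RSI and Likert are due at V5 and V6, and section 6.5.2 bases the V6 judgement of maintenance on them. Section 8.3.2 presents the follow-up efficacy data that were collected, descriptively only.

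**Weeks 0 to 6.** Section 6.4.6 leaves retention after a non-permitted medication to the investigator. Section 8.2 says that patients who worsened and needed additional therapy or a changed omeprazole dosage "will be considered major violators but remained in the study until visit V4 and entered into the ITT efficacy analysis".

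**The concern.** The plan asks how much rescue, permitted or not, is used in follow-up, and then stops observing a patient at the first non-permitted intake. That intake is recorded. Anything taken afterwards, omeprazole included, is not, so frequency, timing and dose are cut off for exactly these patients.

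The same event replaces the week-18 RSI and Likert scores with an earlier reading or with nothing. Taking another product to control GERD is a sign that the effect was not maintained, so the data are lost because of the outcome. If untreated controls relapse more often, more is lost in that arm. Its rescue use, and possibly its V6 symptoms, then look milder than they were, and the second randomised contrast (Gerdoff v no treatment) is drawn towards zero. Section 2.1 places the 12-week maintenance period within the primary objective, so these summaries will be read even though they are not tested.

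**Working it through.** **1. The plan's own figure.** The only sample size stated is for the RSI change to V4 (section 8.1): delta 3.6, SD 5, 80% power, two-sided 5%. By the normal approximation, n per arm = 2 × (1.960 + 0.842)² × 5² / 3.6² = 30.3, so 31 per arm and 62 in total; 62 / 0.80 = 77.5, so 78. This reproduces. It concerns V4, before follow-up starts, so the present point does not touch it.

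**2. Size of the follow-up arms.** No responder rate is given. Assuming 30% to 70% of the 39 Group 1 patients respond, 11.7 to 27.3 enter follow-up, or about 6 to 14 per arm. One patient is then about 17% to 7% of an arm.

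**3. Assumptions for the loss.** The documents give no relapse or rescue rates, so all of these are illustrative:
- relapse probability p: 0.40 in controls, 0.20 on Gerdoff;
- mean week-18 RSI: 8 if maintained, 18 if relapsed, so the true difference is 10 × (0.40 − 0.20) = 2.0;
- relapse day uniform over 84 days, and omeprazole on half of the days after relapse;
- a share q of relapsers takes another product and is gone 7 days after relapse.

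**4. Rescue days.** A fully observed relapser contributes 0.5 × 42 = 21 days. A removed relapser contributes 0.5 × (7 − 7²/(2 × 84)) = 3.35 days. The mean per relapser is 21(1 − q) + 3.35q, multiplied by p for the arm mean. The proportion lost is q × (21 − 3.35)/21 = 0.84q.

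**5. V6 RSI with no usable early reading.** Arm mean = 8 + 10p(1 − q)/(1 − pq).

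| q | Omeprazole days, control v Gerdoff (true 8.4 v 4.2) | Arm difference understated by | V6 RSI difference (true 2.0) |
|---|---|---|---|
| 5% | 8.0 v 4.0 | 4% | 1.96 |
| 10% | 7.7 v 3.8 | 8% | 1.91 |
| 25% | 6.6 v 3.3 | 21% | 1.75 |
| 50% | 4.9 v 2.4 | 42% | 1.39 |

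**6. Effect of early readings.** If a share r of removed patients has an early reading of 18, replace q by q(1 − r) in step 5. With q = 50% and r = 50% the difference is 1.75 rather than 1.39; with r = 100% it is 2.0. Early readings recover none of the rescue-day loss.

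**7. Side by side.** For weeks 0 to 6, section 6.3.3 requires discontinuation after other GERD therapy, section 6.4.6 leaves it to the investigator, and section 8.2 says certain such patients remained until V4. These three cannot all hold.

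**The case against.** The case on the other side has real force.

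- **Relapse by itself removes nobody.** A reader might infer that V6 scores are lost in all patients who relapse. The documents do not support that. Every follow-up patient is supplied with omeprazole for the full 12 weeks, may use it if symptoms worsen, and stays in. Only a relapser who takes something else is removed. This stands and limits the point.
- **The share affected may be small.** With permitted rescue already in hand, few patients may turn to another product, and nothing in the documents supports a share as high as 50%. At 5% to 10% the losses are minor. This stands.
- **An early V6-type reading may preserve the RSI contrast.** It may, wholly or in part (step 6), but it depends on best effort.
- **The arm ordering for rescue survives.** A reader might infer that recorded rescue would be lowest where need was greatest. At arm level the illustration does not show that: controls stay at twice Gerdoff at every q. The absolute days and their difference shrink.
- **Continued observation has its own problem.** A week-18 RSI obtained on an extra product may be good because of that product. In the extreme, if every such patient scored 8, the difference would be 2.0 × (1 − q): 1.80 at 10% and 1.00 at 50%, lower than in step 5. That score would still describe the patients' actual state at week 18, but it must not be read alone. The gain from continued collection is clearest for rescue use.
- **Treatment failure already covers the outcome.** It does so for a yes/no maintenance count. It supplies neither rescue days nor RSI and Likert scores.
- **Weeks 0 to 6 are not a settled precedent.** Agreed: the sections conflict, so section 8.2 cannot simply be copied.

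**Conclusion.** The point holds within limits. For follow-up patients who take a GERD product other than omeprazole, the plan stops collecting data needed for its own rescue objective and endpoint, and replaces week-18 RSI and Likert scores with an early reading at best. The trigger is related to outcome, so rescue use, and possibly V6 symptoms, can be understated more in the arm that relapses more.

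The size is unknown. On the assumptions in the working, the rescue-day difference is understated by about 4%, 8%, 21% or 42% when 5%, 10%, 25% or 50% of relapsers take another product. The V6 RSI difference falls from 2.0 to 1.96, 1.91, 1.75 or 1.39 if there is no usable early reading, and by less if there is one. Small arms mean that one or two removals would be visible.

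A reader might go further and doubt the trial's main result. The documents give no ground for that: the V4 primary analysis and N = 78 are untouched, and follow-up efficacy is descriptive. The change is still worth making, because it is cheap and lets the plan measure what it sets out to measure.

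**What to change.** - **Sections 6.4.6 and 6.5.1 (rescue note to the flow-chart).** Separate protocol-violator status from the end of data collection. State that diary, V5 and V6 (RSI, Likert, safety) continue on schedule after the violation unless consent is withdrawn. Count the patient as not maintained. Where possible, also take RSI and Likert at the time of the violation.
- **Section 6.3.3.** Align the return of the diary at discontinuation with this.
- **Section 8.3.2.** Tabulate follow-up rescue over V4 to V6 for all re-randomised patients, with omeprazole and other products separate, and per day observed for anyone who still leaves early. Show V6 RSI next to the not-maintained count, because it may reflect the extra product.
- **Sections 6.3.3, 6.4.6 and 8.2.** Reconcile what they say on whether a patient who takes other GERD therapy stays in the study.

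No view is taken on which treatment such a patient should receive or which clinical discontinuation rule is right; the change concerns data collection only.

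The cost is wording. V5, V6 and the diary are already scheduled, and no patients or planned visits are added; an RSI and Likert at the violation is one short extra questionnaire contact for a few patients. The small downside is that V6 RSI in these patients needs the accompanying count to be interpretable.
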